With the exception of assessment of daily MVPA by accelerometer, all outcomes will be assessed at the University of Kansas Medical Center, in Kansas City, KS. Cognitive function, cardiovascular fitness, and quality of life will be assessed at the Center for Physical Activity and Weight Management (CPAWM) and all neuroimaging outcomes will be assessed at Hoglund Brain Imaging Center (HBIC), which is located next door to the CPAWM. Our experience with similar trials suggests these assessments, which will be completed by trained staff blinded to condition, will

require ~2.5 hrs. to complete. Some assessments will only be collected on a sub-sample of participants.

Primary Outcome- MVPA.

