Quality of Life. Quality of life will be assessed at baseline, 6, and 12 mos. with the Personal Well-Being Index-Intellectual Disability(PWI-ID)^{62, 63}. This instrument contains 7 items, each corresponding to a quality of life domain: standard of living, health, life achievement, personal relationships, personal safety, community-connectedness, and future security. Cronbach alpha of 0.76, and 1- to 2-wk. test-retest reliability of 0.58 have been reported in adults with IDD⁶². The PWI-ID scale differs from the original Personal Well-Being Index (PWI-A) in that it incorporates a pre-testing protocol to determine whether, and to what level of complexity, respondents are able to use the scale. The ID version also uses more simple and concrete wording. An additional question which asks how happy or sad the respondent is with life as a whole is included. A reduced choice format, illustrated as a series of outline faces, from very sad to happy, is provided to enhance comprehension and substitutes for the Likert scale used in the PWI-A version⁶³.

Neuroimaging (Sub-sample).. Neuroimaging measures of brain volume i.e. structural MRI, functional connectivity, i.e. resting state MRI (rsMRI), blood flow, i.e. arterial spin labeling (ASL), and spectroscopy (MRS) will be assessed at baseline, 6, and 12 mos. utilizing the scan parameters currently implemented by the NIAD and ABC-DS Structural MRI imaging has elucidated the specific brain regions impacted by dementia in DS. These grey matter changes are detectable prior to the development of signs of clinical dementia^{64, 65} and have been impacted by cardiovascular fitness/MVPA⁵⁶. Structural MRI is a feasible test in adults with DS. In a recent review of 9 trials that used rsMRI in adults with DS⁶⁶, 4 reported no scanning issues, and in the remaining 5, ~17% of participants were excluded due to motion artifact with those who have more severe intellectual

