disabilities being more likely to move during the scan. However, only individuals with mild to moderate intellectual disabilities will be included in this study, which will decrease the likelihood of motion during the scan. To further reduce motion during the scan and to minimize attrition, participants will have the option to partake in a practice session before the scheduled baseline scan. For the practice session, participants will be introduced to Hoglund study team members, lie in the scanner with the appropriate head coil while 3 minutes of a study sequence runs. The practice session will last ~15 minutes and a safety screener will be completed at the beginning of the practice session. Volumetric analyses of overall and regional, e.g. hippocampus, brain volumes will be performed using FreeSurfer segmentation using the longitudinal processing stream ⁶⁷, which is currently being implemented for the Alzheimer's Disease Center registry data at KUMC. rsMRI examines functional connectivity within and between brain networks. Individuals with DS show increased connectivity between networks compared to typically developing adults which has been hypothesized to reflect increased compensatory brain activation ⁶⁸. Pre-processing of rsMRI data will be performed for each participant using Analysis of Functional NeuroImages (AFNI, Medical College of Wisconsin). The rsMRI images will be realigned to the first slice collected in each scanning session to correct for motion. The images will be spatially smoothed with a 4 mm Full Width Half Maximum (FWHM) Gaussian blur. Functional and anatomic images obtained in each session will be aligned and normalized to a DS brain template ⁶⁸. An ASL sequence will be collected to measure changes in blood flow that may be related to increased fitness associated with physical activity. ASL analyses will be performed using the ASL Toolbox ⁶⁹ with Statistical Parametric Mapping version 12 software (SPM12) ⁷⁰ and applying methods that are currently implemented for the Alzheimer's Disease Center registry at KUMC.

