6.2.2 Enrollment, Baseline, and/or Randomization

Enrollment

Enrollment is defined as the date in which a participant has signed a consent form, passes the DSQIDD turned in a physician consent form.

Baseline Assessments.

Baseline Assessments will take place within two weeks of starting the intervention and will include

- Medication review
- MVPA using accelerometer
- Cognitive Function
- Cardiovascular Fitness
- Quality of Life Questionnaire
- Anthropometrics
- Physical Function (Sub-sample).

- Caregiver Outcomes (Sub-sample).
- Optional practice MRI
- MRI (Sub-sample).
- Adverse Events Review

Randomization

Randomization will take place within 2 weeks before the start the intervention.

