8.3 Data Analyses

Our primary aim is to assess daily MVPA (min.) among the RL, RH, and UC arms at baseline, 3, 6, 9, and 12 mos. and obtain effect sizes for change in MVPA over 12-mos. We will calculate the mean and standard deviation and 95% confidence intervals of daily MVPA at each time point for all 3 groups, as well as for the change from baseline to each time point. This descriptive information will be summarized graphically which will aid in determining if, and when, differences in MVPA arise among and across the 3 groups. The corresponding effect sizes at each time point will be calculated as the differences in the mean divided by the common standard deviation. We will also estimate the correlation of MVPA over time within individuals. This information will be critical to identifying whether single point in time or longitudinal assessments will be utilized to identify the sample size needed for future large-scale confirmatory trials. We will subsequently run a repeated measures ANOVA comparing the change in baseline at each time point across the three groups using a linear mixed model approach with an autoregressive correlation structure over time. The model will include a main effect of group and time and a group by time interaction which will provide an estimate of the treatment effect when modeling longitudinally. The data from this trial will provide solid preliminary data to determine the potential for an effect and inform the best design to employ in subsequent trials.

Our first secondary aim will assess the impact of MVPA across the RL, RH, and UC arms on cardiovascular fitness, quality of life, cognitive function, and brain parameters (whole and regional brain volume, functional connectivity, cerebral blood flow) at baseline, 6, and 12 mos. We will estimate the correlation of change in MVPA on changes in cardiovascular fitness, quality of life, cognitive function, whole and regional brain volume, functional connectivity and cerebral blood flow at 6 and 12 mos. This analysis will be completed with the total sample, irrespective of study arm. Thus 80 participants will provide at least 80% power to detect correlation of 0.31 or higher or -0.31 or lower with a type I error rate of 5%. Sixty subjects (25% loss to follow-up) will still allow us to detect a correlation of 0.36 or higher or -0.36 or lower with 80% power and type I error rate of 5%.

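### The 80- and 60-participant power figures in Section 8.3 are applied to MRI outcomes that are collected only in a sub-sample of unstated size

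*Combined protocol and SAP*

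**What the plan says.** Under the first secondary aim, Section 8.3 (Data Analyses) lists the brain measures (volumes, connectivity and blood flow) alongside cardiovascular fitness, quality of life and cognition. Changes in all of these, at 6 and 12 months, are to be correlated with change in MVPA. The section then states: "This analysis will be completed with the total sample, irrespective of study arm". The power claim follows directly: "Thus 80 participants will provide at least 80% power to detect correlation of 0.31 or higher or -0.31 or lower", with a 5% type I error. The only reduction considered is attrition: "Sixty subjects (25% loss to follow-up) will still allow us to detect a correlation of 0.36 or higher or -0.36 or lower". No outcome is excepted.

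Elsewhere the imaging is described differently. The opening of the assessments part of Section 5 says: "Some assessments will only be collected on a sub-sample of participants". The imaging paragraph there is headed "Neuroimaging (Sub-sample", and the baseline visit list in Section 6.2.2 has "MRI (Sub-sample". The 6-month list (Section 6.2.3) and the 12-month list (Section 6.2.5) carry the same label. Fitness, quality of life and cognition carry no such label.

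No section says how many participants will be scanned, how they will be chosen, or what correlation that number could detect.

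**The concern.** The power statement rests on numbers of participants that the imaging outcomes will not have if MRI is truly done in a sub-sample. A reader of Section 8.3 would credit the brain correlations with 80% power at 0.31, or at 0.36 after 25% loss.

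This matters because the brain measures are named in Secondary Aim 1, and Section 2.1 presents them as evidence that will help shape a later trial. If the imaging correlations come out null, a reader relying on Section 8.3 could take correlations of 0.31 to 0.36 as having been fairly tested when they were not.

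**Working it through.** **Inputs.** All are from Section 8.3 unless noted.
- Type I error 5%. Two-sided is implied because both positive and negative correlations are given, so z = 1.960.
- Power 80%, so z = 0.842. The sum of the two is 2.802.
- n = 80, or n = 60 after 25% loss (80 × 0.75 = 60).
- MRI sub-sample size: not given anywhere.

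**Formulas** (Fisher z, one Pearson correlation).
- Detectable r = tanh(2.802 / √(n − 3))
- Required n = (2.802 / atanh(r))² + 3
- Power = Φ(atanh(r) × √(n − 3) − 1.960)

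**Step 1: reproduce the plan's figures.**
- n = 80: tanh(2.802 / √77) = 0.309. Power at 0.31 is 80.3%.
- n = 60: tanh(2.802 / √57) = 0.355. Power at 0.36 is 81.2%.

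A simulation of the t test gave 80.8% and 81.8%. A one-sided test would give detectable values of 0.276 and 0.318, so the plan used a two-sided test. The arithmetic is correct for 80 and 60.

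**Step 2: how many usable MRI pairs would the same claims need?**
- r = 0.31: (2.802 / 0.3205)² + 3 = 79.4, so 80 pairs. If a detectable r that merely rounds to 0.31 is accepted, 77 pairs suffice (detectable r 0.315 to three decimals, just under 0.315 unrounded).
- r = 0.36: (2.802 / 0.3769)² + 3 = 58.3, so 59 pairs. With the same rounding allowance, 57 pairs suffice (detectable r 0.364).

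**Step 3: convert to baseline scans under the plan's 25% loss.**
- 59 / 0.75 = 78.7, so 79 of 80 scanned.
- 57 / 0.75 = 76, so 76 of 80 (95%) with the rounding allowance.

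**Step 4: sensitivity to the unknown size.** The sizes below are assumptions, since the document gives none.

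| Assumed analysable pairs | Detectable \|r\| at 80% power | Power at 0.31 | Power at 0.36 |
|---|---|---|---|
| 60 | 0.355 | 68% | 81% |
| 50 | 0.387 | 59% | 73% |
| 40 | 0.431 | 50% | 63% |
| 30 | 0.492 | 38% | 50% |
| 20 | 0.591 | 26% | 34% |

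If instead 60, 50 or 40 participants were scanned at baseline and 25% were lost, about 45, 37 or 30 pairs would remain. The detectable correlations would then be 0.41, 0.45 and 0.49.

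**Step 5: scan exclusions.** None of these figures allows for scans lost to motion. On the nine trials in the review it cites, Section 5 reports: "4 reported no scanning issues, and in the remaining 5, ~17% of participants were excluded due to motion artifact". It also expects less of this here, because of the level of disability enrolled, "which will decrease the likelihood of motion during the scan". Any such loss would lower n further, by an amount the document does not settle.

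**The case against.** The strongest reply is that the sub-sample might be nearly the whole trial, so the claim cannot be called false. For the 0.36 figure this has force, because 59 usable pairs would be enough. The requirement of 79 scanned also depends on the full 25% loss. At an assumed 10% loss, 59 / 0.90 = 65.6, so 66 scanned would do; with no loss, 59 would do. So the 0.36 figure is unverifiable for MRI rather than shown to be wrong. But Section 8.3 itself ties that figure to 25% loss, and nothing in the document suggests that the sub-sample is that large. The 0.31 figure has almost no such room, since it needs 77 to 80 pairs.

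A second reply is that the total-sample phrase is there to say that the arms are pooled, not that everyone is scanned. That is a fair reading of the phrase. It does not rescue the power statement, which goes on to use 80 and 60 with attrition as the only reduction.

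A third is that little depends on the figure. The trial is early-stage, the analysis is described as estimating correlations, and Section 8.1 justifies the sample size by the precision of mean MVPA. This stands, and it limits the seriousness: no estimate is biased and no decision rule uses these correlations. Still, the plan chose to make a power claim for these outcomes, and the claim should match the data to be collected.

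**Conclusion.** The concern holds. Section 8.3 gives the imaging correlations a power that the described data collection does not support. The figures are correct, and stand, for fitness, quality of life and cognition.

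For MRI, the 0.31 claim fails for any sub-sample more than marginally below 80. The 0.36 claim holds only with about 57 to 59 usable pairs, which under the plan's 25% loss means scanning about 95% or more of participants. How far power actually falls short cannot be stated, because the sub-sample size is missing; the values at 60 pairs and below show sensitivity only. The conclusion assumes a two-sided 5% test of a single Pearson correlation, which matches the plan's own numbers.

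The inconsistency affects one group of secondary outcomes and leaves the primary aim untouched. It should be corrected before the imaging results are interpreted.

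**What to change.** 1. Limit the total-sample wording and the 80/60-participant power statement in Section 8.3 to fitness, quality of life and cognition.
2. For the MRI outcomes, do one of the following:
   - state the planned sub-sample size and how participants are selected, and give the detectable correlation at that size after expected loss and scan exclusions; or
   - state that the imaging correlations are exploratory, reported as estimates with confidence intervals and without a power claim.

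This is a change of wording and needs no added participants or scans. The only cost is a less favourable stated figure, or none, for the imaging outcomes.

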burden (physical, emotional, financial). Caregiver stress will be assessed using the Caregiver Self-Assessment Questionnaire (CSAQ), which is a caregiving-specific measure of psychosocial stress and is an appropriate measure for depression screening⁷⁷. Caregiver quality of life will be assessed using the Adult Carer Quality of Life Questionnaire (AC-QoL)⁷⁸, which covers eight different domains for caregivers: support for caring; caring choice; caring stress; money matters; personal growth; sense of value; ability to care; and caregiver satisfaction.

Feasibility. Retention. Retention will be measured as the percentage of participants who complete the 12 mo. intervention, defined as completing the 12 mo. outcome assessments. Session attendance. Session attendance for both group MVPA and individual education/support sessions from baseline to 12 mos. will be obtained from records maintained by the health educator, and expressed as the percent of possible sessions. Attendance at group MVPA sessions will be defined as being logged in to the video conference and remaining on the screen for the entire 30-min session. Attendance at individual support/education sessions, for the both exercise and UC conditions, will be defined as answering the Zoom call, and being present on screen for the entire session. Use of recorded exercise sessions (RL and RH only) will be tracked using Dropbox which provides information on how many times each user watched a video. Safety. Safety will be measured by number of participants reporting a serious adverse event, i.e., any untoward medical occurrence that results in death, is life-threatening, requires inpatient hospitalization or results in persistent or significant disability/incapacity.

Descriptive outcomes. To characterize our study sample, we will measure weight, height and waist circumference in participants at baseline, 6, and 12 mos. Weight will be measured in light clothing on a calibrated scale (Model #PS6600, Belfour, Saukville, WI) to the nearest 0.1 kg. Standing height will be measured with a portable stadiometer (Model #IP0955, Invicta Plastics Limited, Leicester, UK). BMI will be calculated as weight (kg)/height (m²). Waist circumference will be assessed using the procedures described by Lohman et al.⁷⁹.

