8 STATISTICAL CONSIDERATIONS

8.1 Sample Size and Randomization

Eighty participants will be randomized in a 2:2:1 manner to RH (n=32), RL (n=32) and UC (n=16), respectively. We except a standard deviation in daily MVPA of ~ 10 min. for our primary endpoint (12 mos.) based on 12 mo. data from adults with DS who participated in our weight management trial in adults with IDD (DK83538, PI [name]). We will be able to estimate the mean MVPA at each time point (baseline, 3, 6, 9 and 12 mos.) with 99% confidence within ± 5 min. for the RH and RL groups with 32 participants, and with 98% confidence with 24 participants, i.e. allowing for a 25% loss to follow-up. We will be able to estimate the mean MVPA at each time point with 94% confidence within ± 5 min. for the UC group with 16 participants, and with 89% confidence with 12 participants, i.e. allowing for 25% loss to follow-up). Thus, we will have precision to estimate the intervention effects even with a 25% loss to follow-up.

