Our second secondary aim will determine the feasibility (retention, session attendance, use of recorded sessions (RH/RL only), and safety) of RL, RH, and UC arms. We will estimate the proportion of participants retained, session attendance, use of recorded sessions and safety, i.e. significant adverse events across the 12 mo. trial, the proportion that adhere to treatment within each arm. Within the RL and RH arms, 32 participants allow us to estimate these proportions with a margin of error no greater than 0.09. Within the UC group, 16 participants will allow us to estimate these proportions with a margin of error no greater than 0.125.

For all analysis we will explore the impact of demographic characteristics such as gender, and racial/ethnic subgroups.

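### The feasibility margins of error of 0.09 (n=32) and 0.125 (n=16) are single worst-case standard errors with no confidence level; at 95% the worst-case margins are 0.173 and 0.245

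*Combined protocol and SAP*

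**What the plan says.** The second secondary aim is feasibility and safety by arm. Section 8.3 introduces the quantities to be estimated: "We will estimate the proportion of participants retained, session attendance, use of recorded sessions and safety". It adds the proportion adhering to treatment within each arm. Two precision statements follow:

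- Remote Low and Remote High: "Within the RL and RH arms, 32 participants allow us to estimate these proportions with a margin of error no greater than 0.09".
- Usual Care: "16 participants will allow us to estimate these proportions with a margin of error no greater than 0.125".

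Neither gives a confidence level, an assumed proportion or a formula.

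The Feasibility paragraph in Section 5 defines the measures. On retention it says: "Retention will be measured as the percentage of participants who complete the 12 mo. intervention". Session attendance is "expressed as the percent of possible sessions". Safety is the number of participants with a serious adverse event. Use of recordings (Remote Low and Remote High only) is tracked through Dropbox as the number of times each user watched a video.

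Elsewhere the plan does attach a level to its precision figures. Section 8.1 gives 99% confidence, within 5 minutes of daily activity, "for the RH and RL groups with 32 participants, and with 98% confidence with 24 participants", and 94% "for the UC group with 16 participants, and with 89% confidence with 12 participants". For the primary outcome, Section 8.3 plans the "mean and standard deviation and 95% confidence intervals of daily MVPA at each time point".

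**The concern.** A margin of error is a multiple of the standard error, and the multiple is set by the confidence level. Without a level the figure cannot be interpreted. Here the two values coincide with the standard error itself, which suggests that the multiplier was left out.

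Section 2.1 says that this early stage trial will establish feasibility and inform a later trial. These two sentences are the only precision justification offered for that aim. If someone planning the later trial took them as 95% margins, they would believe that retention in usual care will be known to within 0.125 when the worst-case figure is 0.245. An allowance for attrition could then rest on that belief.

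A second question is whether one bound can cover every item listed, since recordings are logged as view counts and not as a proportion.

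**Working it through.** **Inputs.** Arm sizes 32, 32 and 16 (Sections 8.1 and 8.3). Stated limits 0.09 and 0.125 (Section 8.3). The assumed proportion is not given; because the plan claims an upper bound, the worst case p = 0.5 is used. The level is not given, so 80%, 90% and 95% are shown.

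**1. Reproducing the plan's figures.** The worst-case standard error is sqrt(p(1−p)/n) with p = 0.5.

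- n = 32: sqrt(0.25/32) = 0.0884, which rounds to 0.09.
- n = 16: sqrt(0.25/16) = 0.1250.

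Both stated values are recovered with a multiplier of one.

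**2. Confidence implied.** The multipliers are 0.09/0.0884 = 1.018 and 0.125/0.125 = 1.000, or 69.1% and 68.3% by the normal approximation. The exact binomial probability, at p = 0.5, that the estimate falls within the stated limit is 0.623 for n = 32 (14 to 18 events) and 0.790 for n = 16 (6 to 10 events).

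**3. Worst-case margins at usual levels.** Margin = z × sqrt(0.25/n).

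| Level | n = 32 (stated 0.09) | n = 16 (stated 0.125) |
|---|---|---|
| 80% | 0.1133 | 0.1602 |
| 90% | 0.1454 | 0.2056 |
| 95% | 0.1732 | 0.2450 |

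At 95% the ratios to the stated values are 0.1732/0.09 = 1.92 and 0.2450/0.125 = 1.96. Other 95% methods give maximum half-widths of 0.164 and 0.220 (Wilson) and 0.181 and 0.253 (Clopper-Pearson). Pooling the two remote arms (n = 64) gives 0.122 at 95%. None of these returns the stated pair.

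**4. When the limits would hold at 95%.** Solving 1.96 × sqrt(p(1−p)/n) ≤ limit gives p ≤ 0.073 or p ≥ 0.927 for n = 32, and p ≤ 0.070 or p ≥ 0.930 for n = 16. The plan's own loss allowance of 25% (Section 8.1) implies retention of 0.75, where the 95% margins are 1.96 × sqrt(0.75 × 0.25/32) = 0.150 and 1.96 × sqrt(0.75 × 0.25/16) = 0.212.

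**5. Numbers that the stated limits would require.** n = 0.25 × (z/limit)²:

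| Level | Limit 0.09 | Limit 0.125 |
|---|---|---|
| 80% | 51 | 27 |
| 90% | 84 | 44 |
| 95% | 119 | 62 |

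These only show the size of the misstatement; they are not a proposal to enlarge the trial.

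**6. Comparison with Section 8.1.** With a standard deviation of 10 and a half-width of 5 minutes, 5/(10/sqrt(n)) is 2.83, 2.45, 2.00 and 1.73 for n = 32, 24, 16 and 12. On the t distribution these correspond to 99.2%, 97.8%, 93.6% and 88.9%, matching the plan's 99, 98, 94 and 89%. The step from standard error to confidence level was therefore taken there.

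**7. Which measures the bound can cover.** Retention, incidence of serious adverse events and the proportion adhering are proportions of participants, so sqrt(0.25/n) applies. Attendance is a fraction between 0 and 1 for each participant; its standard deviation cannot exceed 0.5, so the same worst-case standard error applies to the mean. A count of views has no upper limit, so the bound does not apply to it unless the count is reduced to used or not used.

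**The case against.** The standard error is computed correctly, and the plan never says 95%. The precision levels in Section 8.1 range from 89% to 99%, so there is no house convention from which to borrow 95%; the twofold figure depends on the reader supplying it. This stands as a qualification. It does not rescue the sentence, because the limits are also exceeded at 80% and 90%, and a margin with no level is incomplete on any reading.

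Nothing in the plan depends on the two numbers, and intervals computed from the data will show the real precision. That is true, and it limits the consequence.

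On recordings, the Dropbox counts would readily give the proportion of participants who used any recording, and the bound would then hold. This is fair: the defect is that the summary measure is not specified, and the bound is not necessarily wrong for it.

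Replacement figures need care too. The normal-approximation values are slightly smaller than the exact half-widths in step 3. For mean attendance with an estimated standard deviation (divisor n − 1), the maximum is 1.96 × 0.5/sqrt(31) = 0.176 and 1.96 × 0.5/sqrt(15) = 0.253. Section 5 lets one study partner support several adults in the same arm, and exercise sessions are held in groups, so outcomes may be correlated and the true margin larger. These points argue for stating the assumptions beside any new figure; they do not support the present ones.

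**Conclusion.** The concern holds. The stated margins are one worst-case standard error each, with no multiplier and no level. If 95% is intended, precision is overstated by a factor of about 1.8 to 2.0 depending on the interval method. The 95% figures assume p = 0.5, independent participants and full arm sizes. For measures available only in completers after 25% loss (24 and 12 participants), they would widen to 0.200 and 0.283; retention keeps the full denominator. A rare outcome such as serious adverse events may meet the stated limits, but the plan claims them for every listed proportion. The primary aim, the sample size and the Section 8.1 precision statement are unaffected. This should be fixed because it is a demonstrable misstatement about a declared aim.

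**What to change.** In Section 8.3, do one of the following:

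- **State the level and restate the figures.** For example: for retention, incidence of serious adverse events, the proportion adhering and mean session attendance (fraction of possible sessions per participant), the 95% margin of error under the normal approximation, at the worst case and with participants treated as independent, is at most 0.174 in each remote arm (n = 32) and 0.245 in usual care (n = 16). These are 0.1732 and 0.2450 rounded up. If exact intervals will be reported, give the exact half-widths instead.
- **Relabel.** Keep 0.09 and 0.125 but call them maximum standard errors.

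In either case, say how use of recordings in the remote arms will be summarised. If it is the number of views, report a mean with a 95% confidence interval and take it out of the bound. If it is the proportion of participants who used any recording, the remote-arm bound covers it.

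The cost is a few sentences and a less favourable stated precision. Sample size, data collection and the primary analysis do not change.
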